PrEP-Pro Study Protocol

Official Title

PrEP-Pro: Adapting a Multicomponent Intervention to Train and Support Providers to Promote PrEP for Adolescent Girls and Young Women in the Deep South

Institution

University of Alabama at Birmingham

Principal Investigators

[name], MPH – University of Alabama at Birmingham

[name], MSPH – University of Alabama at Birmingham

NCT Number: NCT06487390

Version Date: 3 September 2025

Statement of Compliance

This study will be conducted in compliance with the protocol, Good Clinical Practice (GCP), and all applicable regulatory requirements, including NIH and UAB IRB regulations.

Protocol Summary

This study evaluates PrEP-Pro, a multicomponent training intervention designed to increase PrEP prescribing among Family Medicine (FM) residents providing care to adolescent girls and young women (AGYW) in Alabama. PrEP-Pro integrates provider education, sexual history-taking training, and peer-led support from PrEP Champions. The study will assess feasibility, acceptability, and preliminary effectiveness using a mixed-methods design across up to six FM residency sites.

Study Schema

Phase 1: Development and adaptation with Community and Scientific Advisory Boards' input.

Phase 2a: Pre-test at 2 sites with 2 PrEP Champions and 8–12 residents.

Phase 2b: Pilot test at up to 6 sites with 12 Champions and 72 residents over 6 months.

Data collection: Surveys, EMR review, Champion logs, and in-depth interviews.

Introduction / Background

Black adolescent girls and young women (AGYW) in the U.S. South are disproportionately affected by HIV, with rates nearly 9 times higher than White peers. Despite the proven efficacy of pre-exposure prophylaxis (PrEP), uptake among AGYW remains low. Barriers include provider knowledge gaps, lack of sexual history-taking, stigma, and competing clinical demands. Family Medicine (FM) residents are uniquely positioned to deliver preventive care, particularly in underserved areas. PrEP-Pro was developed to address these barriers by training FM residents in HIV prevention and supporting sustainable PrEP prescribing practices.

Additional protocol details are available:


Objectives and Endpoints

Primary Objective: To evaluate the feasibility and acceptability of PrEP-Pro among FM residents.

Secondary Objectives: To improve provider knowledge and skills in PrEP prescribing and sexual history-taking; to assess preliminary effectiveness on PrEP prescriptions and HIV/STI testing among AGYW.

Exploratory Objectives: To identify multilevel barriers and facilitators of PrEP implementation using COM-B (Capability, Opportunity, Motivation – Behavior) model and CFIR (Consolidated Framework for Implementation Research).

Specific Aims

HIV disproportionately impacts Black adolescent girls and young women (AGYW) in the Deep South. In Alabama, nearly half of PrEP-eligible adolescents are AGYW, yet none in a recent sample of 429 adolescents had been prescribed PrEP. Barriers include limited provider knowledge, infrequent sexual history-taking, and stigma. Family medicine (FM) residents represent a critical workforce to reduce disparities, but current training does not equip them with the skills or motivation to provide PrEP.

The PrEP-Pro intervention is a multicomponent training designed to improve PrEP prescribing for AGYW by equipping FM residents with knowledge, skills, and peer support. Guided by the COM-B model and CFIR, PrEP-Pro integrates:

1. Education on HIV epidemiology and PrEP.
2. Training in sexual history-taking.
3. Support from trained peer “PrEP Champions.”

Our Specific Aims are:

Aim 1: Adapt PrEP-Pro training materials and tools with input from community and scientific advisory boards, FM residents, and AGYW.

Aim 2: Pre-test PrEP-Pro at two FM residency sites to assess feasibility and acceptability, and refine procedures.

Aim 3: Conduct a six-month pilot test of PrEP-Pro across up to six FM residency sites to evaluate acceptability, feasibility, and preliminary effectiveness. Identify determinants of implementation at the provider, clinic, and system levels through in-depth interviews and CFIR-guided analysis.

Impact:

PrEP-Pro has the potential to transform HIV prevention in the South by training a generation of FM providers to routinely offer PrEP to AGYW, directly addressing a major gap in HIV prevention.

Research Strategy

Innovation

- **Multicomponent intervention:** Combines education, skills training, and peer leadership in a single package.
- **Champion model:** Embeds “PrEP Champions” to sustain practice change, a proven implementation strategy adapted here for PrEP.
- **Implementation science framework:** Uses COM-B and CFIR to design, deliver, and evaluate the intervention.

- **Community-engaged design:** CABs of FM residents and AGYW co-develop content, ensuring contextual relevance.

Study Design and Procedures

A mixed-methods, multi-phase implementation science study:

- **Phase 1:** Development and adaptation of PrEP-Pro with CAB/SAB input and FM resident focus groups.
- **Phase 2a:** Pre-test at two residency training program sites (2 Champions, 8–12 residents).
- **Phase 2b:** Six-month pilot test at up to six sites (up to 12 Champions, 72 residents).

Setting and Sites

- Cahaba Family Medicine Residency Program
- Montgomery Family Medicine Residency Program
- UAB Huntsville Family Medicine Residency Program
- Additional sites as identified

Sites serve diverse patient populations with ≥20% Black patients.

Participants

Eligibility Criteria:

- Licensed FM resident (MD or DO).
- Provides care to AGYW in Alabama.
- Practices at clinic with ≥20% Black patient population.
- Willing and able to provide informed consent.

Sample Size:

- Pre-test: 2 Champions, 8–12 residents.
- Pilot: Up to 12 Champions, ~72 residents.

Intervention: PrEP-Pro

Core Components:

1. **Provider Education:** HIV epidemiology, PrEP indications/efficacy, prescribing practices.
2. **Sexual History Training:** Role-play, scripts, and tools for adolescent-focused sexual history-taking.
3. **PrEP Champions:** Peer residents trained more extensively (~4 hours, 3 sessions) to deliver training, provide ongoing support, and sustain intervention at their sites.

Materials:

- Training PowerPoints, reference “Badge Buddies,” sexual history screening tool, PrEP prescribing guides, and patient-facing handouts.
- Online resource manual (Google Site) with curriculum, troubleshooting guides, and supplemental resources.

Study Procedures**Phase 2a: Pre-test**

1. **Recruitment:** Up to 2 PrEP Champions and 12 residents. Partner program directors nominate potential Champions; those interested contact the study team to complete consent.
Residents invited to participate through training with their residency site. Those interested in participating in the study self-consented and completed the enrollment baseline survey.
2. **Training PrEP Champions:**
 - Three sessions (total ~4 hours).
 - Content: HIV epidemiology, PrEP prescribing, sexual history-taking, role-play.
 - Delivery training: how to teach peers using standard slides and cases.
3. **Resident Training:** Champions deliver two 1-hour sessions to peers over 1 month.
4. **Data Collection:**
 - **Pre/post surveys:** demographics, PrEP knowledge/attitudes, AIM/IAM/FIM, EPAS.
 - **Champion logs:** time spent, resident contacts, support provided.
 - **IDIs:** up to 9 participants (Champions + residents) provide feedback.
 - **EMR review:** de-identified data on PrEP prescriptions, HIV/STI tests (3 months pre- and post-intervention).
5. **Refinement:** Content, tools, and procedures adjusted based on pre-test results.

Phase 2b: Pilot Test

1. **Recruitment:** Up to 12 PrEP Champions and 72 residents. Partner program directors nominate potential Champions; those interested contact the study team to complete consent.
Residents invited to participate through training with their residency site. Those interested in participating in the study self-consented and completed the enrollment baseline survey.
1. **Training:**
 - Champions trained (same as pre-test).
 - Champions deliver two 1-hour sessions to peers.
 - Fidelity monitored via session observation and audio recording; feedback provided.
2. **Ongoing Support:**

- Champions meet biweekly with site administrators/social workers to troubleshoot insurance and workflow issues.
- Champions log PrEP-related activities and resident contacts.
- Peer Champions connected across sites for shared learning.

3. Data Collection:

- **Surveys:** at baseline, 3 months, and 6 months.
- **Champion logs.**
- **IDIs:** with Champions, residents, AGYW patients, and stakeholders (~50 total).
- **EMR review:** 6 months pre- and post-intervention, capturing PrEP prescriptions and HIV/STI testing.

Outcomes

Primary Outcomes:

- Acceptability (AIM, IAM, EPAS).
- Feasibility (FIM, training completion rates, Champion engagement).

Secondary Outcomes:

- Provider PrEP knowledge, attitudes, and willingness to prescribe.
- Frequency of sexual history-taking.
- PrEP prescriptions to AGYW.
- HIV/STI testing for AGYW encounters.

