3.7 Data Analysis

- **Quantitative:**
 - Descriptive statistics for acceptability/feasibility.
 - Pre/post changes in prescribing/testing assessed using Wilcoxon signed-rank, McNemar's test, logistic regression, and Poisson regression.
 - Adjustments for provider demographics and site-level factors.
- **Qualitative:**
 - Thematic analysis of IDIs guided by COM-B and CFIR.
 - Triangulation across surveys, EMR, and interview data.

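### Preliminary effectiveness on HIV/STI testing rests on 6 months before versus 6 months after training, with no control and no calendar-time term, so background trend and season are mixed into the estimated change

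*Combined protocol and SAP*

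**What the plan says.** Objectives and Endpoints lists, as a secondary objective, "to assess preliminary effectiveness on PrEP prescriptions and HIV/STI testing among AGYW". Under Study Procedures, Phase 2b, Data Collection, the EMR review covers "6 months pre- and post-intervention, capturing PrEP prescriptions and HIV/STI testing". The Phase 2a pre-test has the same structure with 3 months on each side. The pilot is sized at "up to 12 Champions, 72 residents", across at most six sites.

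The analysis, in section 3.7, reads "Pre/post changes in prescribing/testing assessed using Wilcoxon signed-rank, McNemar's test, logistic regression, and Poisson regression". The only adjustment named is "Adjustments for provider demographics and site-level factors".

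The document describes no untrained comparison site or resident, no staggered start, no calendar-time or seasonal term and no check of the pre-training trend. It also has no statement of limitation about background change. Human Subjects and Oversight says the EMR data are aggregated and de-identified, but not at what level or time interval. The Dissemination Plan says the findings will inform a proposal for a hybrid effectiveness-implementation trial.

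**The concern.** With one window before training and one after, the pre/post indicator coincides with everything else that differs between the windows. Three things stand out. Testing may already be rising. Two neighbouring six-month windows cover largely different halves of the year. Residents are also more senior in the second window than in the first. Demographics and site factors are essentially the same in both windows, so adjusting for them cannot absorb change over time. Triangulation with surveys and interviews, also planned in section 3.7, supplies no estimate of what testing would have been without training.

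At stake is the reading of a stated secondary objective, and possibly an overstated effect carried into the next proposal.

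**Working it through.** **Inputs.** From the documents: 6+6 months, up to six sites, about 72 residents, 0 of 429 adolescents prescribed PrEP in the cited sample. The documents state no alpha, effect size, testing rate, encounter volume or trend, so there is no planned figure to reproduce. Everything else below is assumed.

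**1. Spurious ratio with zero training effect.** With a one-month training gap, the window midpoints are 7 months apart. At monthly growth g, the post/pre ratio is R = (1+g)^7.

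**2. Chance of p<0.05 with zero training effect.** Let p0 = 0.20 and p1 = 0.20 × R, with n encounters per window. Then z = (p1 − p0) / √{[p0(1−p0) + p1(1−p1)]/n}, and the chance is Φ(z − 1.96) + Φ(−z − 1.96).

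Example, g = 1%, n = 1,000: p1 = 0.2144; SE = √[(0.1600 + 0.1684)/1,000] = 0.0181; z = 0.0144/0.0181 = 0.80; chance = 12.5%.

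| Growth per month | Per year, (1+g)^12 − 1 | R | n = 500 | n = 1,000 | n = 2,000 |
|---|---|---|---|---|---|
| 0.25% | 3% | 1.018 | 5.2% | 5.4% | 5.9% |
| 0.5% | 6% | 1.036 | 5.9% | 6.8% | 8.6% |
| 1% | 13% | 1.072 | 8.7% | 12.5% | 20.3% |
| 2% | 27% | 1.149 | 20.9% | 36.7% | 63.0% |

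**3. Cross-check with a different test.** Compare two Poisson counts by z = ln R / √(1/μ0 + 1/μ1), with μ1 = μ0 × R. Take adjacent windows (midpoints 6 months apart), 72 residents with 10 to 40 AGYW encounters each, and 10% to 30% tested. Then μ0 runs from 72 × 10 × 0.10 = 72 to 72 × 40 × 0.30 = 864 tests. The chance of p<0.05 is 5% with no growth, 6-17% at 10% a year and 9-49% at 20% a year. The pattern is the same.

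**4. PrEP prescriptions.** Zero of 429 has an exact two-sided 95% upper limit of 1 − 0.025^(1/429) = 0.86%, so counts are likely to be very low. With 2 to 10 prescriptions assumed in the pre window, the Poisson formula (rough at such counts) gives 5-6% at 20% annual growth. Proportional growth is therefore mainly a problem for testing.

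**5. Precision cost of adjustment.** Use least squares on monthly points with equal weights, independent errors of variance σ² and a one-month gap.
- Crude 6+6: variance of the step = σ²(1/6 + 1/6) = 0.333σ².
- Crude 18+6: σ²(1/18 + 1/6) = 0.222σ².
- Linear month added: variance is multiplied by 5.20 at 6+6 (SE × 2.28) and by 2.51 at 18+6 (SE × 1.59).
- Linear month and one seasonal pair at 18+6: 0.657σ². Against crude 18+6, √(0.657/0.222) = 1.72. Against the planned crude 6+6, √(0.657/0.333) = 1.40.

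The longer baseline is therefore what makes trend adjustment affordable.

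**The case against.** The strongest reply is about weight. Effectiveness is secondary and already called preliminary, and the primary outcomes do not use this comparison. The label stands as mitigation, but it signals imprecision and does not remove a bias with a direction.

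Several stronger readings are tempting, and the documents do not support them:
- A reader might infer that the plan commits to crediting any rise to PrEP-Pro. Section 3.7 states no hypothesis, alpha or success criterion. It leaves background change unseparated and makes no claim about it.
- A reader might infer that the EMR data arrive as two totals. That is not stated, and the paired tests in section 3.7 suggest paired units.
- A reader might infer that this estimate will size the hybrid trial. The Dissemination Plan says only that findings inform a proposal.
- A reader might take the false-positive rate to be high. That depends on growth of 1% a month or more, which is 13% a year upward. At 3-6% a year the rate stays close to nominal.

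The remedy has limits too. Nothing in the documents shows how far back each site's records go or what extraction costs. A linear month term does not model resident turnover or seniority, and an outside event at the time of training would still fall into the step. Clinic-level counts may include clinicians outside the study. Precision is lost: with 20% tested, 1,000 encounters per window and a true ratio of 1.3, the crude comparison has z = 0.06/0.0188 = 3.20 and power of about 89%. Dividing z by 1.40 gives 2.28 and about 62%. This is why the adjusted estimate belongs beside the crude ratio and should not replace it.

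Finally, the document refers to a published protocol article for further detail. It was not available, so the point concerns this document only.

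**Conclusion.** The point holds in limited form. As written, the pilot cannot separate a training effect on HIV/STI testing from background trend or season. How much this matters is unknown, because the documents give no trend, testing rate or volume. Under the assumptions in the working, the chance of a nominally significant change with no training effect runs from 5-9% at slow growth (0.25-0.5% a month) to 9-20% at 1% and 21-63% at 2%. The consequence is confined to a secondary, preliminary objective and mainly to testing. For PrEP prescriptions, sparse counts make ordinary growth a small issue, although an outside step change would still look like a training effect. The point does not show that any PrEP-Pro effect will be spurious, and it does not call for a control arm in a feasibility pilot.

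**What to change.** 1. Ask each site for the same clinic-level EMR counts by calendar month: AGYW encounters, HIV tests, STI tests and PrEP prescriptions. Go back about 18 months before training where records allow, and cover the 6 months after.
2. For HIV and STI testing, report beside the crude pre/post ratio a step estimate from a quasi-Poisson model with encounter offset, site effects, linear month and one seasonal pair. State in advance that a crude rise which disappears after trend adjustment will not be attributed to PrEP-Pro.
3. Show PrEP prescriptions as monthly counts only.
4. State that, without a control, outside events and resident turnover or seniority cannot be excluded.

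This is a cheap improvement. It costs a longer EMR query, one extra model and a wider interval. The adjusted standard error is about 1.4 times that of the planned 6+6 crude comparison, or about 1.7 times the crude one on the same 18+6 months, under the assumptions of step 5 in the working. Where a site cannot supply the longer baseline, give its monthly counts and the limitation statement.

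### Does the primary feasibility outcome need a named attendance source and a written rule for training completion?

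*Combined protocol and SAP*

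**What the plan says.** The Primary Outcomes list gives feasibility as "Feasibility (FIM, training completion rates, Champion engagement". Section 3.7 (Data Analysis) plans "Descriptive statistics for acceptability/feasibility" and sets no completion target.

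The Study Schema lists the sources: "Data collection: Surveys, EMR review, Champion logs, and in-depth interviews". For the pre-test (Phase 2a) the Champion logs hold "time spent, resident contacts, support provided". For the pilot (Phase 2b), under Ongoing Support, "Champions log PrEP-related activities and resident contacts", and under Training, "Fidelity monitored via session observation and audio recording; feedback provided".

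The pre-test timetable reads "Champions deliver two 1-hour sessions to peers over 1 month". The pilot has the same two sessions but states no delivery period. Pilot recruitment is "Up to 12 PrEP Champions and 72 residents".

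**The concern.** Feasibility is half of the primary objective, and completion is one of its three components. The Feasibility of Intervention Measure (FIM) comes from surveys, and Champion engagement can be read from the logs. Completion alone has no stated source.

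The rule is open too. With two sessions, completion could mean either one or both. Phase 2b gives no period. Champions are themselves peer residents with three training sessions of their own, so it is not explicit whether they belong in the count.

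A definition can be settled at reporting, but attendance that nobody recorded cannot be reliably recovered. If only session totals were kept, completion would be available as a range. If the rule were chosen after attendance was known, the result would be less convincing. The findings are meant to support a proposal for a larger trial.

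**Working it through.** The plan states no completion figure, target or precision, so there is nothing to reproduce. The check has two parts: what each source could hold, and what would be lost if attendance by individual were missing.

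**Sources compared**

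| Source | Described content | Could it hold attendance? |
|---|---|---|
| Pre-test surveys | Demographics, knowledge and attitudes, acceptability and feasibility scales | Not listed |
| Pilot surveys (baseline, 3 and 6 months) | Not itemised | Cannot be excluded |
| Champion logs | Time, contacts with residents, support, PrEP activities | Yes: the Champion runs the session |
| Pilot observation and audio recording | Fidelity | Yes: an observer is present |
| EMR review | Prescriptions and tests | No |
| Interviews | Up to 9 people in the pre-test, about 50 in the pilot | Not for all residents |

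None is named as the attendance source, but at least two could carry it without a new form. The Human Subjects and Oversight section also has investigators reviewing training fidelity and data completeness.

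**What is lost if only totals are kept**

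Inputs from the protocol: n = 72 residents, 12 Champions, two sessions. Attendance figures are assumed. With a1 and a2 enrolled residents at sessions 1 and 2:

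- both sessions: from max(0, a1 + a2 − n) to min(a1, a2)
- at least one: from max(a1, a2) to min(n, a1 + a2)

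| a1, a2 | Both | At least one |
|---|---|---|
| 54, 54 | 108 − 72 = 36 to 54 (50.0% to 75.0%) | 54 to 72 (75.0% to 100%) |
| 63, 63 | 126 − 72 = 54 to 63 (75.0% to 87.5%) | 63 to 72 (87.5% to 100%) |
| 72, 54 | 126 − 72 = 54 to 54 (75.0%) | 72 to 72 (100%) |

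The range narrows as attendance rises. It vanishes if everyone attended one session, as would happen if residents enrolled at the first session (one possible reading of the recruitment text, not stated). With records by individual there is no range under any pattern.

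**Counting Champions**

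Assume all 12 Champions complete and are additional to the 72. The rate becomes (x + 12)/84 for x completing residents:

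- x = 36: 48/84 = 57.1%, against 50.0% (+7.1 points)
- x = 54: 66/84 = 78.6%, against 75.0% (+3.6 points)
- x = 63: 75/84 = 89.3%, against 87.5% (+1.8 points)

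The protocol points away from this pooling. The Study Schema, Sample Size and Recruitment entries all count Champions and residents separately, and Champions have their own component in the same outcome line.

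**Period**

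Phase 2a gives one month for delivery. Phase 2b is a six-month pilot, which sets an outer limit.

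**The case for a change.** The strongest case for a change is that the omission is real, concerns a primary outcome, and is cheap to close: one attendance field and a sentence of definition. Recruitment adds some weight. Residents are invited through training at their programme, so sessions may include people who did not enrol. Head counts would then mix enrolled and other attendees and could not give even the bounds above for enrolled residents. Nor do the named sources settle the matter: the log entries describe contacts, not attendance, and observation is stated to be for fidelity.

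The textual point stands: this document neither defines completion nor names its source. It is a short protocol, however, and refers the reader to a separately published protocol paper for more detail. That paper was not available here, so silence in this text is weak evidence that no attendance record exists. The possible mixing of enrolled and other attendees is a reason to record names, which a team reporting completion rates would ordinarily do. Counts of residents invited and survey response rates would be useful in a report, but they are separate matters and do not follow from an undefined completion rate.

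**Conclusion.** No change to the plan is called for. This is missing detail that analysts can fill sensibly: count enrolled residents, state whether completion means one or both sessions, and show Champions separately. Completion is one of three feasibility components and is reported descriptively with no threshold, so no decision rule turns on the choice, and nothing in the document shows that any result would be wrong.

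The 36-to-54 range rests on two assumptions that the protocol does not make: 75% attendance at each session, and records limited to totals. The conclusion rests on attendance being recorded by individual in practice, in the logs, the observation records or elsewhere. If only anonymous totals had been kept, the report would need to say so and give completion as a range, provided that the totals covered enrolled residents only.
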